### **13.4 Primary Objective, Endpoint(s), Analysis Plan**

A primary endpoint of the study is safety through the 6 month follow-up visit. Safety of the three escalating dose of WOKVAC will be assessed by adverse events as per CTCAE v4.0.

The type and grade of toxicities noted during the immunization regimen will be summarized. The duration of toxicities will also be summarized using descriptive statistics such as mean and standard deviation. All adverse events noted by the investigator will be tabulated according to the affected body system. The frequency and severity of adverse events will be summarized with a proportion and a 95% confidence interval. Despite lack of randomization, the incidence and severity of toxicity will be compared between successive dose groups using nonparametric test with the understanding that due to small sample size per dose group such test will have limited sensitivity to detect any small to moderate differences. These tests will be performed without adjustment for multiplicity of testing.

Demographic and baseline characteristics obtained at enrollment will be summarized in tabular or graphical formats with descriptive statistics.

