### **13.3 Accrual and Feasibility**

The study will accrue 30 evaluable patients with up to 12 patients in each dose arm. We anticipate up to 15% of enrolled patients may fail to receive all three vaccinations and the 1 month post vaccine follow-up.

For information regarding the study population (including gender and minority considerations) please see Section 4.3 Inclusion of Women and Minorities.

In order to meet the primary objective of this study, AE information is collected at each of the study visits and reviewed by the study team on a regular basis. If patients are unable to complete to the one month post vaccination follow-up visit, AE information may be collected by phone if possible. For secondary objectives, the research samples will be batched after each cohort to achieve consistency in the assays.

When we batch the research samples we will run the baseline time point and post vaccine time point(s) for a patient (usually 4-5 patients at one time). With this we are looking at results of an individual (comparing their IFN-g response to their baseline) therefore the results can be analyzed together.

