Analyses of the above secondary endpoints will be descriptive in nature by necessity. Despite lack of randomization, we will compare the immunologic efficacy between the 3 dose levels data using linear dose-response relationship with a regression analysis. Normalizing transformation will be used as well if necessary. The linear regression model will have a 0.80 power to detect an anticipated effect size (defined as  $R_2/(1-R_2)$ ) of 0.281 according to the level 0.05 F-test, given the sample size of 30.

Once the dose escalation is completed, key study personnel in concert with the NCI/DCP staff will review the toxicity, immunogenicity, antibody immune response, memory T cell response, Treg, and MDSC, and make a recommendation for a phase 2 dose. Statistical tests will only be advisory due to lack of randomization and limited sensitivity of such tests given the small sample size for each dose group. We may seek other experts in this deliberation.

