### **13.7 Reporting and Exclusions**

If a patient drops from the study prior to becoming evaluable for immune responses, data will still be used to assess the safety of WOKVAC. In the event that an enrolled patient drops from the study for a reason other than a dose limiting toxicity (as defined in Section 8.5.1) prior to completing the 1-month post-vaccination follow up visit, then an additional patient will be enrolled onto the study, up to a maximum of 12 patients per dose level.

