### **13.9 Evaluation of Response**

The number of patients traditionally required to gather preliminary data on the safety of a dose in a phase I study is less than the number needed to evaluate immunologic responses and differences in the immunologic responses between cohorts of patients. Since Phase I tumor vaccine studies to date have proven to be relatively free of serious toxicity, the defining endpoint that would move a study forward to a more extensive phase II efficacy trial will likely be immunogenicity. In order to have meaningful immunologic data, the study will accrue 30 evaluable patients (10 patients per dose arm). When accrual is complete, we will: (1) determine if the WOKVAC vaccine elicits specific cellular and humoral immune responses for each antigen, and persistent antigen specific memory T cells can be detected and (2) which dose is most immunogenic. We expect that there may be differences in immune response between dose-levels. Moreover, the dose-level that is determined to be the most biologically relevant in terms of stimulating immunity may not be the highest dose.

Immune responses will be evaluated for patients who complete the vaccination series with both a baseline and a one month post vaccination series blood draw. Durability of generated immune responses will be evaluated in patients who complete the vaccination series with both a baseline and a 6 month post vaccination series blood draw.

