### **13.10 Interim Analysis**

There will be ongoing monitoring of toxicity data and the attribution as well as immunologic efficacy. The DCP Protocol Template  
Protocol Template Version: 8.4  
10/29/15

secondary endpoints of immunogenicity, T-cell memory, Treg and MDSC levels will be analyzed after each dose level.

After each dose group, interim analysis of toxicity will be reviewed by key study personnel in consultation with NCI/DCP staff before proceeding to the next dose level. Dose escalation and accrual at current dose will follow the criteria described above in section 8.5.1 and statistical tests described above in sections 13.1 and 13.4.

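### Toxicity is compared only between adjacent doses; an added final-analysis trend test across the three ordered arms would be more sensitive to a rise with dose, mainly for lower-grade events

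*Combined protocol and SAP*

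**What the plan says.** Safety is the primary endpoint. Section 13.4 tabulates adverse events, gives proportions with 95% confidence intervals, and adds one formal comparison: "the incidence and severity of toxicity will be compared between successive dose groups using nonparametric test". That means Arm 1 v Arm 2 and Arm 2 v Arm 3. The test is not named and no significance level is given. The section warns that "due to small sample size per dose group such test will have limited sensitivity to detect any small to moderate differences" and adds: "These tests will be performed without adjustment for multiplicity of testing". It plans no Arm 1 v Arm 3 contrast and no trend test.

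Section 13.5 treats the immune endpoints differently. It compares the three dose levels "using linear dose-response relationship with a regression analysis", with 0.80 power at an effect size of 0.281 and N = 30. It also says that statistical tests are only advisory for the phase 2 dose.

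Section 13.10 says that escalation and accrual follow the criteria in 8.5.1 and the "statistical tests described above in sections 13.1 and 13.4".

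**The concern.** The doses are ordered, and toxicity that depends on dose would be expected to rise across them. Two adjacent-pair tests split such a rise into two smaller steps and test each on about 20 patients. Neither uses the largest contrast, Arm 1 v Arm 3. The caveat in 13.4 names sample size as the only reason for limited sensitivity, but the same patients could be analysed more efficiently, as 13.5 already does for a secondary endpoint.

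At stake is the balance of evidence when the phase 2 dose is recommended. Under 13.5, toxicity is weighed there beside immunogenicity. The immune data would arrive with an ordered-dose test and the toxicity data with two less sensitive pairwise tests.

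**Working it through.** **Inputs.** Section 13.9 plans 10 evaluable patients per arm. The upper bound is "up to a maximum of 12 patients per dose level" (13.7). Section 13.3 states: "We anticipate up to 15% of enrolled patients may fail to receive all three vaccinations" and the 1-month follow-up; 10/0.85 = 11.8, so a safety set of up to 12 per arm is realistic, since 13.7 keeps dropouts in it. Assumptions, because the plan is silent: Fisher's exact test for the pairs, two-sided 0.05 per test, and all toxicity rates.

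**1. The plan's own power figure.** Noncentral F with 1 and 28 df, λ = 0.281 × 30 = 8.43, gives power 0.800. A three-group test with 2 df would give 0.690. The stated 0.80 is therefore for a one-degree-of-freedom ordered-dose test. No power is stated for toxicity.

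**2. One table by hand.** Take 0/10, 3/10 and 6/10 patients affected. Fisher gives p = 0.21 (0 v 3) and p = 0.37 (3 v 6). For the exact Cochran-Armitage test with scores 0, 1, 2, the statistic is 0×0 + 1×3 + 2×6 = 15; given 9 events in all, its null mean is 9. Of the C(30,9) = 14,307,150 equally likely allocations, 37,200 + 5,850 + 450 + 10 = 43,510 give 15 or more. The two-sided p is 2 × 43,510 / 14,307,150 = 0.006. At 10 per arm, a Fisher pair needs a gap of at least 5 patients (0 v 5; 1 v 7; 2 v 8) to reach 0.05.

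Scores 0, 1, 2 suit these doses: 300/150 = 600/300 = 2, so the arms are equally spaced in log dose.

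**3. Power by full enumeration** of the 11 × 11 × 11 = 1,331 possible outcomes. The pairwise plan counts as a success if either test has p ≤ 0.05, unadjusted as planned.

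| True rates, Arms 1/2/3 | Either pair | Exact trend |
|---|---|---|
| 10/20/30% | 3% | 12.5% |
| 10/30/50% | 11% | 43% |
| 20/40/60% | 11% | 42% |
| 10/35/60% | 18% | 63% |
| 10/40/70% | 27% | 81% |
| 20/50/80% | 26% | 80% |
| 10/50/90% | 56% | 99% |

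Under 10/40/70%, 55% of trials are significant on trend only and 1% on pairs only. With 12 per arm: 19% v 50% for 10/30/50% and 44% v 84% for 10/40/70%.

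**4. False positives.** At flat rates of 20%, 30% and 50%, the exact trend test rejects in 2.5%, 3.1% and 4.1% of trials. Trials significant on a pair only add 1.1%, 1.8% and 1.8%. The chance that any of the three tests is significant is therefore 3.7%, 4.9% and 5.9%.

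**5. Effect of the stopping rule.** Under 8.5.1, three non-exempt attributable grade 3 events at a dose, or one attributable grade 4, end accrual to the study. Arm 3 is thus normally reached only with at most 2 such grade 3 events in each earlier arm. If the rates were 10/30/50%, the chance is P(≤2 of 10 at 10%) × P(≤2 of 10 at 30%) = 0.930 × 0.383 = 0.36. The tables that remain carry little information: 0/1/2 gives trend p = 0.28, 0/1/3 gives 0.10 and 0/2/3 gives 0.14.

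**6. Non-monotone patterns.** For 10/70/40% the pairs reach 67.5% and the trend test 20%; for 10/60/10%, 63% and 0.1%.

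**7. The escalation cross-reference.** Section 13.1 describes the arms and refers to 8.5.1 for sufficient evidence of safety; it contains no statistical test. The tests in 13.4 compare dose groups, so none can exist at the Arm 1 to Arm 2 decision, when only Arm 1 has data. At the Arm 2 to Arm 3 decision the Arm 1 v Arm 2 test exists, but no text says how its p value acts beside the 8.5.1 counts.

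**The case against.** The strongest reply is that little depends on these tests. Escalation has a count rule, the tests are advisory for the phase 2 dose, and 13.4 already requires tabulated grades and proportions with confidence intervals; reviewers would see 0/10, 3/10, 6/10 without a p value. Section 13.8 expects no significant toxicity at any dose. Cohorts are sequential and not randomised, so irregular patterns between arms are plausible, and there the pairs do better.

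Most of this stands, and it limits the point. It does not remove it: the plan chose to test toxicity formally, and for an ordered rise it chose the less sensitive form. Lower-grade events are plausible, since 6.2 lists injection-site redness, fatigue and headache as likely.

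A reader might infer more than the documents support:

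- That a steady rise is always missed by the pairs and always found by a trend test. The table shows otherwise: at 10-point steps both usually fail, and at 40-point steps the pairs succeed in 56% of trials.
- That a rise would be reported as no difference. Nothing in the plan tells anyone to read a non-significant result that way, and 13.4 warns of limited sensitivity.
- That the pairs should be dropped. Step 6 of the working argues against that.

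**Conclusion.** The point holds as a moderate improvement to the analysis plan. Part of the limited sensitivity that 13.4 attributes to sample size comes from testing adjacent pairs only. For steady rises of 10 to 30 points per dose step with 10 per arm, an exact trend test has roughly three to four times the chance of significance, without exceeding 5% error at the flat rates checked. The absolute gain is large only for steps of about 25 to 30 points; at 20 points or less the trend test itself stays below 50%.

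The gain is mainly for lower-grade or any-grade toxicity and for the final phase 2 dose discussion. It does not help the escalation decisions, because a three-dose trend cannot be computed before Arm 3 has data. All figures rest on assumed rates, Fisher tests and two-sided 0.05.

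The wording of 13.10 is a separate inconsistency and does not depend on any power figure. A reader might infer that 8.5.1 alone governs escalation; the documents do not say so, since 13.10 also cites statistical tests and requires review with NCI/DCP staff.

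**What to change.** In 13.4, add one prespecified exact trend test over the three ordered doses at final analysis as the main between-dose toxicity comparison: Cochran-Armitage for patient-level incidence and Jonckheere-Terpstra for worst grade per patient. State the scores, the two-sided level and the event definition, including an any-grade or lower-grade incidence. Keep the successive pairwise comparisons as supportive results and name the test used. Say that power remains low for rises of 20 points or less per step.

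The authors should reconcile 13.10, 13.1, 13.4 and 8.5.1, so that it is clear which tests, if any, are meant at each escalation decision and how they relate to the count rule and the planned review.

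The cost is wording only: no extra patients, visits or data. The small downsides are one more unadjusted advisory test for each outcome (for incidence, see step 4 of the working) and insensitivity of the trend test to non-monotone patterns, which the retained pairs cover.

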### **13.5 Secondary Objectives, Endpoints, Analysis Plans**

- To determine the immunogenicity of WOKVAC Th polyepitope plasmid based vaccine in patients with breast cancer at 3 escalating doses.
- To evaluate for the presence of a Th2 immune response by antibodies against the WOKVAC antigens
- To determine whether a WOKVAC Th polyepitope plasmid based vaccine elicits a persistent memory T cell response.
- To evaluate whether WOKVAC vaccination modulates T regulatory cells (Treg) and myeloid derived suppressor cells (MDSC).
- To determine a recommended phase 2 dose for further breast cancer prevention studies.
- To assess the long-term effects of 3 escalating doses of a deoxyribonucleic acid (DNA) plasmid

based vaccine encoding three breast cancer antigens (IGFBP-2, HER2, and IGF-1R) in patients with breast cancer, for 5 years from enrollment to satisfy the evaluation requirements for the Food and Drug Administration (FDA)

Immune responses as measured by IFN-g ELISPOT will be summarized with mean and standard deviation or median and range over time, the change over time will be summarized with graphs, and also analyzed using linear mixed-effects regression models with normalizing transformation if necessary. Each patient would be given a value at each immune evaluation that is the sum of the median response to HER2, IGFBP-2 or IGF1R, and a composite median would be calculated for each WOKVAC dose level.

Antibody immunity will be assessed as an additional measure of a Th2 response. A humoral immune response will be measured by ELISA and serum antibody avidity for IGFBP-2, HER2, and IGF-1R (using ELISA) to determine an avidity index (AI) before and after vaccination. Low avidity antibodies will have an AI <30%, moderate avidity antibodies 30-50% and high-avidity antibodies 51-100%. Patients will be considered to have developed an antibody response if antigen specific IgG antibodies are both detectable and have moderate to high avidity.

Memory T cell response will be summarized with proportion over time, and the change over time will be summarized with bar charts, and analyzed using generalized linear mixed effects regression models with suitable link function.

Treg cell, and MDSC levels will be summarized with mean and standard deviation or median and range over time, the change over time will be summarized with graphs, and analyzed again using linear mixed-effects regression models with normalizing transformation if necessary.

Analyses of the above secondary endpoints will be descriptive in nature by necessity. Despite lack of randomization, we will compare the immunologic efficacy between the 3 dose levels data using linear dose-response relationship with a regression analysis. Normalizing transformation will be used as well if necessary. The linear regression model will have a 0.80 power to detect an anticipated effect size (defined as  $R_2/(1-R_2)$ ) of 0.281 according to the level 0.05 F-test, given the sample size of 30.

Once the dose escalation is completed, key study personnel in concert with the NCI/DCP staff will review the toxicity, immunogenicity, antibody immune response, memory T cell response, Treg, and MDSC, and make a recommendation for a phase 2 dose. Statistical tests will only be advisory due to lack of randomization and limited sensitivity of such tests given the small sample size for each dose group. We may seek other experts in this deliberation.

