**2.3.3. Development of Th1 T cell immunity and persistent memory.** Our immunologic analysis will focus on analyzing Type I immune responses via IFN- $\gamma$  ELISPOT as Type I immunity has been associated with beneficial clinical outcome in breast cancer. We will, however, analyze both Th1 and Th2 responses to the WOKVAC antigens prior to and after active immunization. We have performed extensive screening of immunity across multiple breast cancer antigens and have found subtle difference between endogenous immune responses identified in breast cancer patients compared to age matched volunteer women. In population based screening studies of 49 class I epitopes derived from 6 breast cancer associated antigens immune responses directed against those antigens were found equally in breast cancer patients ( $n=20$ ) and volunteer controls ( $n=20$ ). In general, median incidence of IFN- $\gamma$  epitope specific responses were low with a median of 40% of volunteer donors demonstrating no response (range 5-58%) and a median of 33% of breast cancer patients demonstrating no response to a particular antigen (range 10-55%). The magnitude of IFN- $\gamma$  responses was greater in the volunteers compared to patients although the difference did not reach statistical significance ( $p=0.45$ ). When IL-10 responses for each patient were evaluated in the context of the IFN- $\gamma$  response, significantly ( $p<0.0001$ ) higher IFN- $\gamma$ /IL-10 ratios were observed among volunteer control patients compared to breast cancer patients. We have identified that some epitopes of self-antigen elicit primarily Th2 immunity and if such epitopes are included in a vaccine will inhibit the development of Th1 response and vaccine efficacy. For this reason we will explore the evolution of the Th1/Th2 ratio for the vaccine components during the course of active immunization. Maintenance of a Th1 dominance and the development of immunologic memory after cancer vaccination have been shown to be associated with a positive clinical outcome. We will evaluate whether there is antibody development by ELISA to support the vaccine as being predominantly Th1.

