## 9. CORRELATIVE/SPECIAL STUDIES

### 9.1 Rationale for Methodology Selection

#### 9.1.1. Immunogenicity of the 3 doses will be evaluated by an assessment of the generation of IGFBP-2,

HER2, and IGF-1R specific T cells (both Th1 and Th2).

Cellular immune response will be defined by the magnitude of the Th1 (IFN-gamma (g)) vs. Th2 (IL-10) antigen specific immune response using ELISPOT. Successful immunization will be defined by generating a protein specific IFN-g precursor frequency greater than 1:20,000 PBMC for each antigen. In patients with pre-existent immunity, responses must augment over 2 times baseline for immunization to be considered successful.

Exploratory analysis will assess whether patients maintain a Th1 dominant immune response to all three antigens over time.

Antibody immunity will be assessed as an additional measure of a Th2 response.

A humoral immune response will be measured by ELISA and serum antibody avidity for IGFBP-2, HER2, and IGF-1R (using ELISA) to determine an avidity index (AI) before and after vaccination. Low avidity antibodies will have an AI <30%, moderate avidity antibodies 30-50% and high-avidity antibodies 51-100%. Patients will be considered to have developed an antibody response if antigen specific IgG antibodies are both detectable and have moderate to high avidity.

- 9.1.2. To detect persistent T cell memory, flow cytometry panels will be used to evaluate antigen specific central and effector memory phenotypes prior to vaccination and at 1 and 6 months after immunizations.
- 9.1.3. To detect modulation of Tregs and MDSC with vaccination, levels over the course of immunization will be assessed by flow cytometry of PBMC.

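### The antibody endpoint is defined only as a yes/no response with an avidity cut and no baseline condition, so it can misclassify in either direction, and no analysis of IgG level or avidity on the full scale is named

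*Combined protocol and SAP*

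**What the plan says.** Sections 9.1.1 and 13.5 give antibody its role: "Antibody immunity will be assessed as an additional measure of a Th2 response". Both have IgG and the AI measured by ELISA before and after vaccination, for IGFBP-2, HER2 and IGF-1R. Both set three avidity classes: low ("Low avidity antibodies will have an AI <30" per cent), moderate (30-50%) and high (51-100%). The endpoint rule is then: "Patients will be considered to have developed an antibody response if antigen specific IgG antibodies are both detectable and have moderate to high avidity".

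Section 13.6 restates the rule differently. It names an IGFBP-2 response only, and it asks for moderate avidity without mentioning high avidity.

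For the other markers, 13.5 is fuller. IFN-g ELISPOT, Treg and MDSC each get summaries on the measured scale, graphs and a linear mixed model. Memory T cells get a generalised linear mixed model. Antibody gets the classification and nothing more.

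Two uses of the result are stated. Section 2.3.3 says: "We will evaluate whether there is antibody development by ELISA to support the vaccine as being predominantly Th1". Section 13.5 lists antibody immune response among the data reviewed when the phase 2 dose is recommended. It also says of dose comparisons in general that "we will compare the immunologic efficacy between the 3 dose levels data using linear dose-response relationship with a regression analysis", and it calls these analyses descriptive and the tests advisory.

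**The concern.** The objective in 13.5 is to look for the presence of a Th2 response through antibodies. Low-avidity IgG bears on presence, yet the rule scores it the same as no IgG at all.

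The rule also speaks of a response having developed but sets no condition on the baseline value. The IFN-g rule in 9.1.1 and 13.6 does: with pre-existing immunity, the response must exceed twice baseline. This matters because 2.3 says the three proteins elicit humoral as well as cellular immunity in breast cancer patients, so some participants may enter with antibody.

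With about 10 patients per arm, a responder count that is open to both errors says little about whether the vaccine raised antibody, or at which dose. Rises or falls in IgG within a class are not seen.

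**Working it through.** **1. The rule applied to four kinds of patient (one antigen).**

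| Patient | Before | After | Score under 13.5 | Antibody changed by vaccination? |
|---|---|---|---|---|
| A | no IgG | new IgG, AI 29% | no response | yes |
| B | no IgG | no IgG | no response | no |
| C | IgG, AI in 51-100% | the same | response | no |
| D | IgG, AI in 30-50% | much more IgG, same class | response | yes |

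A and B score alike, as do C and D. A is an undercount of new antibody and C an overcount. The net error depends on how many patients are of type A and type C, and the documents give neither an AI distribution nor a baseline IgG rate.

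**2. The plan's own power figure.** Section 13.5 states: "The linear regression model will have a 0.80 power to detect an anticipated effect size", with the size (R²/(1-R²)) given as a value "of 0.281 according to the level 0.05 F-test, given the sample size of 30". Section 13.9 gives the allocation: "the study will accrue 30 evaluable patients (10 patients per dose arm".

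- Noncentrality = 0.281 × 30 = 8.43, with 1 and 28 degrees of freedom.
- Power from the noncentral F = 0.800. The effect size giving exactly 0.80 is 0.2808, so the figure reproduces.
- R² = 0.281/1.281 = 0.219, so r = 0.468.
- Two dose indicators instead of one linear term would give 0.690. The stated figure is therefore for one linear dose term on a continuous outcome.

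**3. The same effect seen through a yes/no cut, every value measurable.** Model: y = √0.281 × x + e, where x is the standardised dose score and e is standard normal, 10 patients per arm. The cut is placed to give an assumed overall response rate. The plan does not give dose scores, so equal spacing and actual doses (150, 300, 600) were both used. The trend test is Cochran-Armitage (40,000 runs); the exact conditional trend test was fully enumerated. The full-scale power is 0.80 throughout.

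| Responders | Equal spacing | Actual doses | Exact test (both scorings) |
|---|---|---|---|
| 50% | 0.585 | 0.61 | 0.55-0.58 |
| 30% | 0.54 | 0.60 | 0.46-0.54 |
| 20% | 0.48 | 0.55 | 0.35-0.47 |
| 10% | 0.27 | 0.32 | 0.12-0.26 |

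At 50% responders the loss runs from 0.80 - 0.61 = 0.19 to 0.80 - 0.55 = 0.25. It grows as responders become rarer.

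**4. The same effect with a detection limit.** Step 3 lets the full-scale analysis see every value. If IgG is often undetectable, those values are tied for that analysis too. Here values below the limit are set to the limit, and response means detectable. Both outcomes are tested by linear regression. Where two figures are separated by a semicolon they are for equal spacing; actual doses.

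| IgG detectable | Full scale, tied at limit | Yes/no | Gain from full scale |
|---|---|---|---|
| 70% | 0.75-0.77 | 0.47-0.54 | 0.21 (0.75 - 0.54) to 0.30 (0.77 - 0.47) |
| 50% | 0.67; 0.71 | 0.59; 0.60 | 0.08; 0.11 |
| 30% | 0.50; 0.58 | 0.54; 0.58 | -0.04; 0.00 |
| 20% | 0.35; 0.47 | 0.44; 0.52 | -0.09; -0.05 |

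The gain is large when most patients have detectable IgG, moderate at half, and absent or reversed at 30% or fewer. Step 4 takes response as detection alone and does not model the separate avidity condition. A proper censored model was not simulated.

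**The case against.** Three points on the other side have force.

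*The plan does not exclude a full-scale antibody analysis.* Section 13.6 lists IgG antibodies as an immunogenicity measure, and the regression in 13.5, with a normalising transformation, could take IgG level or AI as its outcome. IFN-g has a success definition beside its mixed model, so a responder rule need not be the only analysis. This stands. A reader might infer that the plan rules out analysing the measured values; in fact it is silent. The silence still leaves the choice of antibody outcome open until the data are in hand.

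*The 0.80 is not an antibody figure.* It is a general statement about immunologic efficacy, in analyses the plan calls descriptive and advisory, and no trend test on antibody responders is planned. This stands too. The power figures above only illustrate how much information a cut can discard.

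*The Th1 reading does not rest on antibody alone.* Sections 2.3.3, 9.1.1 and 13.6 also use IL-10 ELISPOT, IFN-g/IL-10 ratios and Th1:Th2 ratios. A reader might infer that dropping low-avidity IgG tilts the trial towards calling the vaccine predominantly Th1. The avidity cut by itself does push that way. But the missing baseline condition pushes the other way, and antibody is only an additional measure, so the documents do not support a claim of net bias towards Th1.

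None of this answers the misclassification shown for patients A and C, or the two versions of the rule.

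**Conclusion.** The concern holds in this form. The only antibody variable that 13.5 and 9.1.1 define is a yes/no response. Applied as written, it can miss new low-avidity IgG and can count unchanged pre-existing IgG. The net direction of error is unknown.

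A reader might also infer a fixed loss of about 20 points of power; the documents do not support a single figure. Illustratively the loss is 20 points or more if most patients have detectable IgG, about 8 to 11 points at half, and nil or reversed at about 30% or fewer. These figures assume a normally distributed underlying outcome, an antibody dose effect equal to the plan's general effect size, and 10 evaluable patients per arm. The documents give no detection rate, responder rate or antibody effect size.

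The case for change rests mainly on the misclassification and the unspecified analysis, and only secondarily on power. It affects a secondary, descriptive endpoint and is a cheap improvement.

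**What to change.** In 13.5:

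- Analyse change from baseline in log IgG for each antigen, regardless of avidity class, at 1 and 6 months by arm, using the IFN-g mixed model. State in advance how values below the detection limit are handled, for example by a censored model.
- Summarise AI where IgG is detectable.
- Report by arm the proportion with any new or increased IgG, with the criterion for an increase stated.
- Keep the avidity-qualified responder rate as a descriptive summary, and add a baseline condition.
- Base the antibody part of any Th1/Th2 statement on all IgG, including low-avidity IgG.

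Reconcile the rule in 13.6 (IGFBP-2 only, moderate avidity only) with 13.5 and 9.1.1.

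Cost: a few sentences and slightly more analysis work. The ELISA and AI values are already to be produced, so no new samples or assays are needed. The Th2 response may look larger or smaller than under the responder cut.
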